3.2.1.1 Definition

a

Table 4	Definition	of Primary	Endpoint
---------	------------	------------	----------

Population:	Evaluable set; Primary analysis population
Endpoint:	Change from baseline (Week 0) to week 13 in airway dynamics, using untrimmed total mucus volume at TLC
Treatment:	Benralizumab 30mg, 3 doses, once every 4 weeks (at baseline [V1], Week 4 [V2] and Week 8 [V3])
Intercurrent events:	Participant withdrawal, IPD, use of prohibited medicines/substances, asthma exacerbation (Participant with exacerbations will be excluded from the primary analysis set)

Population-level	Unadjusted within participant difference in total mucus volume (specific airway volume)
summary:	measured at TLC, calculated as the mean change from baseline (Week 0) at Week 13
	$(\pm 5 \text{ days})$

3.2.1.2 Derivations

Change from baseline for each participant will be derived as follows:

mucus volume at Week 13- mucus volume at Week 0

Mean change will be derived across all participants.

3.2.1.3 Handling of Dropouts and Missing Data

The analysis populations will only include participants who have completed 3 doses of study intervention and have baseline and post-benralizumab treatment study evaluation (PROs, CT scans, and spirometry tests). To that end, participants withdrawing before Week 13 and participants with missing mucus volume measurements at Week 0 or Week 13 will not be included in the analysis.

3.2.1.4 Primary Analysis of Primary Endpoint

The distribution of mucus at Weeks 0 and Week 13 will be graphically displayed in a boxplot. If there is evidence of skewness, data will be log-transformed prior to analysis.

For the primary objective, the analysis will be a paired t-test to determine if there is a significant difference between the mean of mucus volume at Week 0 versus Week 13, irrespective of participant characteristics. The level of significance will be set at 0.05 and so the average mucus volume at Week 0 will be interpreted as significantly different from the average mucus volume at Week 13 if the p-value of the t-test is less than a significance level of 0.05.

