9 STATISTICAL CONSIDERATIONS

9.1 Statistical Hypotheses

For the primary and secondary objectives, measures of mean within subject difference in FRI parameters (enumerated in Table 3) between weeks 0 and 13 the null hypothesis is a difference of 0, an assumption based on existing data described in Section 4.2 suggesting untreated participants are likely to exhibit stable or declining primary endpoint values over a similar (12 week) time period.

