3 STATISTICAL ANALYSIS

This section provides information on definitions, derivation and analysis/data presentation per domain.

All continuous variables, including FRI parameters (Table 2), pre-BD FEV₁, pre-BD FVC, CCI , will be summarized using means, standard deviation (SD) and 95% ranges, or medians and inter-quartile ranges, depending on the distributions of the data. Mean changes from baseline in continuous variables will be reported, including asymptotic 95% confidence interval (CI). Categorical data (eg, CCI

) will be summarized as the number and

percentage among participants with non-missing data. Descriptive statistics will be calculated for the data stratified by gender. Unless otherwise stated, all hypothesis tests are two-sided and all hypothesis tests will be performed at a 5% significance level. Analyses will be carried out for overall participants and subgroups as specified in Section 3.2.1.8. FRI parameters may be log-transformed prior to analysis to reduce skewness.

All report outputs will be produced using SAS® version 9.4 or a later version in a secure and validated environment.

For continuous data, mean, and upper and lower quartiles will be rounded to one additional decimal place compared to the original data. The SD will be rounded to one additional decimal place compared to the original data. Median, minimum and maximum will be displayed with the same accuracy as the original data. For categorical data, percentages will be rounded to one decimal place, percentages will not be shown for 0, decimal places will not be shown for 100%.

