2.11.3 Skewed Data

Mucus volume data that is skewed would be log-transformed according to SAP section 3.2.1. This data can be zero however, so a log plus one transformation will be used if needed. That is, each value of the data will be increased by one and then the log-transformation will be applied. The Skewness of the data is determined by checking box plots of the data and seeing if the mean deviates from the median greatly and if there is asymmetry between the quartiles.

Specific airway volume and airway wall volume are the only other FRI parameters that need to be considered for possible transformation. Should it be determined that a transformation is required the rules in SAP section 3.2.1 should be followed.

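### SAP 3.2.1.4 reads the primary p-value as a difference in average mucus volume even when the test is run on log(x+1) values, which test something else

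*SAP*

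**What the plan says.** **The quantity of interest is on the volume scale.** For the mean within-participant difference, Protocol 9.1 says "the null hypothesis is a difference of 0". SAP 3.2.1.2 subtracts the Week 0 volume from the Week 13 volume and adds: "Mean change will be derived across all participants".

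**The test may be on another scale.** SAP 3.2.1.4 says "If there is evidence of skewness, data will be log-transformed prior to analysis", and then that "the analysis will be a paired t-test to determine if there is a significant difference between the mean of mucus volume at Week 0 versus" the later visit. "The level of significance will be set at 0.05", and under SAP 3, "Unless otherwise stated, all hypothesis tests are two-sided". SAP Addendum 2.11.3 notes that volumes can be zero, so "a log plus one transformation will be used if needed". Skewness is judged by eye from box plots.

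**The reading of the p-value is fixed.** SAP 3.2.1.4 states that "the average mucus volume at Week 0 will be interpreted as significantly different from the average mucus volume at Week 13 if the p-value" falls below the 0.05 level. It makes no exception for transformed data, and Addendum 2.11.3 adds none.

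The visible text has no back-transformation, no geometric-mean or ratio wording, and no rule for the case where the two scales disagree. Sensitivity and supplementary analyses of the primary endpoint are marked not applicable (SAP 3.2.1.6 and 3.2.1.7). SAP 3 does plan mean changes with 95% confidence intervals, without naming the scale.

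**The concern.** Once the data are transformed, the paired t-test asks whether mean log(volume+1) changed. The SAP commits in advance to announcing the answer as a difference between average volumes. The two can part when the shape of the distribution changes between visits, for example when most participants clear some mucus and a few with heavy plugging gain some.

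The p-value carries much of the weight here. The study has one arm, and Protocol 4.2 defines a clinically meaningful change in the primary endpoint as a significant one. The transformed branch is also a live one, because Addendum 2.11.3 was written with zeros and skewness in mucus volume in mind. A significant log-scale result could therefore sit beside a mean volume change near zero, and the written rule would still call the averages different.

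**Working it through.** **The plan's own figure.** The Protocol synopsis gives 29 participants. It cannot be reproduced, because the effect size, SD and power in Protocol 9.2 are blacked out. It is used below only as n; the point does not depend on it.

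**Step 1: the two nulls.**
- Untransformed: E[X13 − X0] = 0.
- Transformed: E[log(X13+1) − log(X0+1)] = 0. The exponential of this quantity is the ratio of geometric means of (volume+1).

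Take lognormal volumes with mean exp(μ + σ²/2). Equal means require μ13 − μ0 = (σ0² − σ13²)/2. With σ0 = 1 and σ13 = 1.5 this is (1 − 2.25)/2 = −0.625. The geometric mean of volume then falls to exp(−0.625) = 0.54 of its baseline while the arithmetic mean is unchanged. For volumes well below 1, log(1+x) is close to x and the two tests nearly agree. The unit therefore matters.

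**Step 2: a constructed data set.** Assumed: 29 baseline volumes at the (i − 0.5)/29 quantiles of a lognormal with log-SD 1 and median 1 unit. The 25 smallest halve and the 4 largest rise 1.62-fold, a factor chosen so that gains and losses cancel.
- Untransformed: mean change 0, p = 1.000.
- log(x+1): mean change −0.167, SD 0.259, t = −0.167/(0.259/√29) = −3.47 on 28 df, p = 0.0017. The back-transformed ratio is exp(−0.167) = 0.85.
- Same pattern at other medians: p = 0.39 at 0.1, 0.068 at 0.3 and 0.00003 at 3.

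**Step 3: how often.** Assumed: n = 29, lognormal baseline with log-SD 1.2, 20% zeros, and 80% of participants falling by 40%. For an unchanged mean the other 20% must rise by 0.8 × 0.4/0.2 = 1.6, that is 160%. Two-sided rejection at 0.05:

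| Median volume (units) | log(x+1) | Untransformed | Excess (points) |
|---|---|---|---|
| 0.01 | 11.8% | 11.3% | 0.5 |
| 0.1 | 14.0% | 11.4% | 2.6 |
| 0.3 | 15.8% | 11.1% | 4.7 |
| 1 | 22% | 11% | 11 |
| 1000 | 42% | 11% | 31 |

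Results that are significant on log(x+1) with the opposite sign to the untransformed mean change occur in 0.0% of trials at medians of 0.3 and below, 0.8% at 1, 4.9% at 10 and 7.7% at 1000. With a milder mix (70% fall by 30%) at median 0.1, rejection is 8.0% against 6.1%.

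**Step 4: another shape change, and a control.** Assumed: correlated lognormal volumes (correlation 0.5 to 0.8), 10% zeros, equal means, and log-SD 1 at Week 0 and 1.5 at Week 13. The log(x+1) test declares a decrease in 11% to 18% of trials at median 0.01, 14% to 23% at 0.1, 29% to 51% at 1 and 63% to 91% at 100. The untransformed test declares one in about 11% to 18%. When both visits have the same distribution, the log(x+1) test rejects in about 4% to 5% in total.

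**The case against.** The case against giving this much weight has five parts.

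1. **It is conditional.** If the box plots do not trigger a transformation, test, null and wording agree. This stands.
2. **The size may be small.** The unit is not given. Addendum 2.11.1 and 2.11.2 ask for extra decimal places for mucus volume, which hints at small values. Below 1 unit the excess over the untransformed test is only a few points in Step 3. This stands, and it bounds the finding.
3. **The scenarios are built to keep the mean fixed.** Nothing in the documents supports a 160% rise in a fifth of participants, and the primary population leaves out those with an exacerbation or lower respiratory tract infection. This stands as a limit on frequency. It does not make the sentence in SAP 3.2.1.4 correct.
4. **The conflict would be visible.** SAP 3 plans mean changes with intervals, and SAP 3.2.1.2 derives them untransformed. This stands in part: the reader might see both, but no rule says which governs, and the rule that is written points to the p-value.
5. **The untransformed t-test is no cure.** It rejects in about 11% of trials in the same scenario. This stands, and it shapes the fix.

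A reader might infer that the log(x+1) test is invalid, or that the two nulls part as soon as individuals change. Neither follows. If participants fluctuate but the Week 0 and Week 13 distributions are the same, both mean differences are zero and the type I error is kept. A rejection under a change of shape reflects a real shift in mean log(volume+1).

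**Conclusion.** The interpretation rule in SAP 3.2.1.4 is wrong as written for the transformed case, and Addendum 2.11.3 does not repair it. The step-2 example suffices to show that the rule can declare the averages different when mean volume has not changed. The fault is in the stated conclusion and not in the test.

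The finding needs two conditions: the transformation is triggered, and the distribution changes shape between visits. How often the wrong conclusion would follow cannot be fixed from the documents. Under the Step 3 assumptions, the excess over the untransformed test is about 0.5 to 5 points at medians of 0.01 to 0.3, about 11 at 1 and about 31 at 1000. A reader might infer from the larger figures that a false claim is likely, or that the p-value would often contradict the direction of the mean change. The documents do not support that: the unit and the response mix are unknown, and opposite-sign results are negligible at medians of 1 or below.

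**What to change.** In SAP 3.2.1.4 and Addendum 2.11.3:

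- State that if log(x+1) is used, p < 0.05 is interpreted only as a change in mean log(volume+1), that is, in the geometric mean of (volume+1). Do not describe it as evidence of a change in average volume.
- Report the back-transformed ratio with its 95% confidence interval.
- Show the untransformed mean change with its 95% confidence interval beside it, each labelled by scale.
- Rest any statement about mean volume on the untransformed estimate and interval, noting that the t-interval is approximate under skewness at n = 29, or on a method suited to skewed data.
- Apply the same wording to the secondary FRI endpoints that may be transformed.

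The cost is wording and one extra row in the primary table; no new data are needed. The downside is that the two scales may visibly disagree.

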3.2.1.5 Secondary Analysis of Primary Endpoint

For the secondary analysis of the primary endpoint a mixed-effects model will be employed to incorporate the repeated mucus volume measurements (corresponding to the different lobes) for each subject. The fitted model will provide estimates of the average change from baseline in mucus volume per lobe, with lobe as a fixed effect and a patient-level random effect to estimate the heterogeneity across lobes. Adjustment will be made for the baseline value of mucus volume.

Equation 1 The mixed-effects model will be as follows:

$$y_{ij} = \beta_0 + \beta_{1j}X_{ij} + \beta_2(baseline)_{ij} + b_{0j} + \varepsilon_{ij}$$

where

• y_{ij} represents change from baseline in mucus volume for subject *i* lobe *j*

- β_0 is the intercept
- β_{1j} is the coefficient for lobe *j*, estimating the average change from baseline in mucus volume for lobe *j*
- X_{ij} is an indicator of whether the mucus volume measurement for subject *i* corresponds to lobe *j*
- β_2 is the coefficient for baseline mucus volume
- $(baseline)_{ij}$ is the baseline mucus volume value for subject *i* corresponding to lobe *j*.
- b_{0i} is the random effect for the *i*th subject
- ε_{ij} is the residual error term

3.2.1.6 Sensitivity Analyses of the Primary Endpoint

Not applicable.

3.2.1.7 Supplementary Analyses of the Primary Endpoint

Not applicable.

3.2.1.8 Subgroup Analyses

The primary endpoint will also be analysed in the following subgroups:

- Mucus plugging status: Participants with (mucus plug score different from 0) or without mucus plugs (mucus plug score equal to 0) identified using CT scans (see Section 8.1.1.2 of the CSP) taken at Visit 1 (Week 0).
- OCS dependency status: OCS-dependent and Non-OCS-dependent participants as defined by the inclusion criteria 4 (see Section 5.1 of the CSP). OCS therapy other than prednisone/prednisolone are allowed provided the average daily dose is equivalent to ≥5 mg of prednisone.

3.2.2 Secondary Endpoint 1 – Change from Baseline in secondary FRI Endpoints

3.2.2.1 Definition

Table 5Definition of Secondary Endpoint 1

Population:	Evaluable set; Primary analysis population
Endpoint:	Change from baseline (Week 0) in secondary FRI parameters
Treatment:	Benralizumab 30 mg, 3 doses, once every 4 weeks (at baseline [V1], Week 4 [V2] and Week 8 [V3])

Intercurrent events:	Participant withdrawal, IPD, use of prohibited medicines/substances, asthma exacerbation (participants with exacerbations will be excluded from the primary analysis set)
Population-level summary:	Unadjusted mean within participant difference, calculated as the mean percent change from baseline (Week 0) at Week 13 (± 5 days), in listed endpoints

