3 OBJECTIVES AND OUTCOME MEASURES

Table 2 Objectives and Outcome Measures

See footnote for abbreviations mentioned on the table below.

Obj	jectives	Outcome measures ^a							
Prir	nary								
dyn ben airv	describe the change from baseline in airway amics after 13 weeks following treatment with ralizumab, using total mucus volume (specific way volume) measurements from untrimmed ways.	Unadjusted mean within subject difference in total mucus volume measured at TLC, calculated as the mean change from baseline (week 0) at week 13 (\pm 5 days).							
Sec	ondary								
1.	To describe the change from baseline in airway dynamics at week 13 following treatment with benralizumab, as measured by secondary FRI endpoints ^b , irrespective of patient characteristics.	Unadjusted mean within subject difference in secondary FRI endpoints (total mucus plugs score at TLC; total air trapping at FRC; trimmed distal iVaww at TLC; trimmed distal siVaw at TLC and FRC; total iVlung at TLC and FRC), comparing baseline (week 0) to week 13 (± 5 days).							
2.	To describe the relationship between airway dynamics and conventional lung function measurements, cross-sectionally (at week 0) and irrespective of patient characteristics.	Correlation between imaging endpoints (primary and secondary FRI endpoints ^b) and pre-bronchodilator forced expiratory volume in 1 second (pre-BD FEV ₁) at week 0. Correlation between imaging endpoints (primary and secondary FRI endpoints ^b) and pre-bronchodilator forced vital capacity (pre-BD FVC) at week 0. Scatter plots of primary and secondary FRI endpoints ^b and mucus plugs score versus conventional lung function measures (pre-BD FEV ₁ and pre-BD FVC) at week 0. Estimated increases in primary and secondary FRI endpoints ^b and mucus plugs score for every one percent increase in pre-BD FEV ₁ and pre-BD FVC at week 0.							

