3.1.10 Sample Size Analysis

3.2 Endpoint Analyses

This section covers details related to the primary, secondary, tertiary, and safety endpoints, including sensitivity and supportive analyses. A summary of the planned endpoint analyses is provided in Table 3.

Details

category	Endpoint	Population	strategy	summary (analysis)	in Section
Primary objec benralizumab	ctive – To describe the c , using measurements f	hange from baselin rom untrimmed air	e in mucus volume at rways at TLC and irre	week 13 following treat spective of patient chara	ment with acteristics
Primary	Change from baseline (Week 0) at week 13 (± 5 days) in untrimmed total mucus volume at TLC	Evaluable set; Primary analysis population	Included in analysis regardless of treatment discontinuation, any IPD or any prohibited medication (treatment policy); Participants with exacerbations are excluded from the primary analysis set	Unadjusted mean within participant difference in untrimmed total mucus volume calculated as the mean change from baseline (Week 0) at Week 13 (± 5 days).	3.2.1
Secondary obj treatment with	jective 1 – To describe t h benralizumab, as mea	he change from ba sured by secondar	seline in airway dynan y FRI endpoints, irresj	nics at Week 13 followin pective of patient charac	g cteristics.
Secondary	Change from baseline (Week 0) at week 13 in primary and secondary FRI parameters ^a	Evaluable set; Primary analysis population	Included in analysis regardless of treatment discontinuation, any IPD or any prohibited medication (treatment policy); Participants with exacerbations are excluded from the primary analysis set	Unadjusted mean within participant difference, calculated as the mean change from baseline (Week 0) at Week 13 (± 5 days), in listed FRI endpoints.	3.2.2
Secondary obj measurements	jective 2 – To describe t s, cross-sectionally (at V	the relationship bet Veek 0) and irrespe	ween airway dynamics ective of patient charac	s and conventional lung cteristics.	function
Secondary	Baseline (Week 0) relationship between pre-BD FEV1 and: In primary and secondary FRI parameters ^a	Evaluable set; Primary analysis population; Baseline endpoints analysis set	Included in analysis regardless of treatment discontinuation, any IPD or any prohibited medication (treatment policy). Participants with exacerbations are excluded from the	 Spearman's rank correlation coefficient Pearson correlation Graphical summary (scatterplots) Regression coefficients with 95% CI 	3.2.3

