3.2.2.3 Handling of Dropouts and Missing Data

The analysis populations will only include participants who have completed three doses of study intervention and have baseline and post-benralizumab treatment study evaluation (PROs, CT scans, and spirometry tests). To that end, participants withdrawing before Week 13 and participants with one of the two FRI measurements missing will not be included in the analysis.

3.2.2.4 Primary Analysis of Secondary Endpoint 1

For each secondary FRI endpoint listed in Table 2, a paired t-test will be used to assess whether there is a statistically significant difference in the mean value at Week 0 versus Week 13, without adjustments for participant characteristics. Data will be log-transformed prior to analysis if there is evidence of skewness.

3.2.2.5 Secondary Analysis of Secondary Endpoint 1

For the secondary analysis of the secondary endpoint, a mixed-effects model will be employed to incorporate the repeated measurements (corresponding to the different lobes) for each subject. The fitted model will be provide estimates of the average percent change from baseline per lobe, with lobe as a fixed effect and a patient-level random effect to estimate the heterogeneity across lobes. The model will adjust for the baseline value of the secondary endpoint. The model will take the same form as described in Equation 1, but with "mucus volume" replaced by the secondary outcome of interest.

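### SAP Table 5 and the text of SAP 3.2.2.5 call secondary endpoint 1 a percent change, while the protocol, SAP Table 3, the paired t-test and Equation 1 use plain change; for mucus plugs score a percent change is undefined at a zero baseline

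*SAP*

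**What the plan says.** The places that define secondary endpoint 1 disagree.

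**Percent change**
- SAP 3.2.2.1, Table 5, population-level summary: "calculated as the mean percent change from baseline (Week 0) at Week 13". The endpoint row of the same table says only change, without percent.
- SAP 3.2.2.5, lobe-level mixed model: the fit is to give "estimates of the average percent change from baseline per lobe, with lobe as a fixed effect".

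**Plain change**
- Protocol Section 3, Table 2: "Unadjusted mean within subject difference in secondary FRI" endpoints. Protocol 9.4.2.2 likewise describes the lobe model as estimating an average change.
- SAP 3.2, Table 3: "Unadjusted mean within participant difference, calculated as the mean change from baseline (Week 0) at Week 13 (± 5 days), in listed FRI endpoints".
- SAP 3.2.2.4: a paired t-test of the mean values at the two visits, after a log transform if the data are skewed.
- SAP 3.2.2.5 again: "The model will take the same form as described in Equation 1". In that equation (SAP 3.2.1.5) the outcome "represents change from baseline in mucus volume for subject" *i* and lobe *j*.

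SAP 3.2.2.2 (Derivations) is marked not applicable, so there is no percent-change formula and no rule for a zero baseline. By contrast, SAP 3.2.1.2 defines change in the primary endpoint as a simple subtraction.

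The SAP expects some baseline plug scores to be zero. SAP 3.2.1.8 makes a score of 0 its own subgroup, and SAP 3.2.2.8 carries that subgroup to secondary endpoint 1.

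**The concern.** Two programmers could produce different tables for the same endpoint and each cite the SAP. For most of the secondary imaging parameters this is a matter of units. For total mucus plugs score it is more than that, for two reasons.

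First, dividing by a baseline of zero gives no value. Protocol 8.1.1.2 describes both a plug count and a 0 to 20 segment score, and either can be zero for a participant or within a lobe. If such records are left out, the ones lost are exactly those that could not have fallen.

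Second, the baseline is itself a noisy count. Using it as the denominator makes the average ratio drift from 1 even when nothing has changed. The study has a single arm, so no control group would show the same drift and allow it to be subtracted.

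**Working it through.** The plan gives no percent-change figure for this endpoint, so there is none to reproduce. Steps 2 to 4 assume no true change.

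**1. Which definition do the documents favour?** Percent appears in one table cell (Table 5 summary) and one sentence (SAP 3.2.2.5). Plain change appears in protocol Table 2, protocol 9.4.2.2, SAP Table 3, the endpoint row of Table 5, the t-test and Equation 1. The addendum does not mention the conflict. Its section 1.3 moves the plug subgroup cut to 4, so participants with a zero score join the group below 4. Its section 2.11.3 gives a zero rule (log of value plus one) for mucus volume only, and names specific airway volume and airway wall volume as the only other candidates for transformation. Plugs score has no zero rule.

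**2. An example that needs no model.** Participant A goes from 1 to 2 plugs, participant B from 2 to 1.
- Mean plain change: (1 + (−1))/2 = 0.
- Mean percent change: (100% + (−50%))/2 = +25%.
- Ratio of group means: 1.5/1.5 = 1, that is, no change.

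**3. Illustration with assumed counts.** Let the baseline Y0 and Week 13 count Y1 be independent Poisson counts with the same mean L. This is an assumption; the documents give no distribution of plug counts.
- Share with undefined percent change: exp(−L).
- Expected percent change in the rest: L × E[1/Y0 | Y0 > 0] − 1.
- For L = 1: exp(−1) = 0.368, and 1 × 0.767 − 1 = −0.233.

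| Mean L | Undefined | Mean percent change in the rest |
|---|---|---|
| 0.5 | 61% | −56% |
| 1 | 37% | −23% |
| 2 | 14% | +15% |
| 4 | 2% | +32% |
| 10 | about 0% | +13% |
| 20 | about 0% | +6% |

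The lower means are the relevant ones for single lobes, the higher ones for participant totals.

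A second illustration lets the mean vary between participants (gamma-Poisson, average total 2 to 40 plugs, shape 0.5 to 2, five equal lobes, 29 participants as in the protocol's primary analysis population):
- Zero baselines: 0.2% to 45% of participants and 4% to 75% of lobes.
- Mean percent change in the rest: about +1% to +19% for totals and −55% to +18% for lobes.
- Mean plain change: −0.04 to +0.05 plugs, with a paired t-test type I error of 0.043 to 0.057.

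**4. A low-noise parameter.** Protocol 4.2 reports siVaw in 22 placebo subjects: mean −3.46%, 95% CI −7.50% to 0.584%.
- Midpoint: (−7.50 + 0.584)/2 = −3.458, which agrees with the stated mean.
- Half-width: (0.584 + 7.50)/2 = 4.042. SD = 4.042/2.080 × √22 = 9.1%.
- Taking 0.091 as the SD of the log change, the spurious mean percent change is exp(0.091²/2) − 1, about +0.4%.

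**The case against.** The strongest reply is that this is a slip of wording. Most of the plan already points to plain change, and a programmer who follows Equation 1 and the t-test as written will never compute a percent change in either analysis. That is largely right, and it limits the point in several ways.

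- A reader might infer that the lobe model is fitted to percent change. The documents do not support that: its equation is in plain change, and only the sentence describing its estimates says percent.
- A reader might infer that the main test is biased. It is not: the t-test compares values at the two visits.
- A reader might infer that every secondary parameter is affected. The zero-baseline problem is shown only for plugs score, and the noise effect is negligible for siVaw. Addendum 1.4 replaces siVaw with untrimmed distal iVaw, for which the documents give no variability.
- A reader might take figures such as −23% as forecasts for this trial. They rest on independent Poisson counts with assumed means. The protocol describes plugs as often persistent, which argues against independent visits.
- A reader might infer that zero-baseline records are excluded by plan. The SAP has no such rule; the handling is simply undefined.

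What the reply does not remove is that Table 5 states the reported summary as a percent, and that this summary cannot be computed for a zero plug score.

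**Conclusion.** The inconsistency is certain and present in the current text. As written, the Table 5 summary cannot be calculated for any participant with a baseline plugs score of zero, nor the percent change described in SAP 3.2.2.5 for any plug-free lobe. What is exposed is the reported estimate, mainly for plugs score, and not the paired t-test p-value.

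The size of any spurious change is uncertain. It could be material at low counts, in either direction, and at very low counts it would look like a treatment benefit. All of those figures depend on assumed plug means and on how variable the counts are between visits. The matter should be corrected, but it does not threaten the primary analysis.

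**What to change.** 1. Delete the word percent from the Table 5 summary and from SAP 3.2.2.5.
2. In SAP 3.2.2.2, state that change is the Week 13 value minus the Week 0 value, per participant and, for the lobe model, per lobe, in line with SAP 3.2.1.2.
3. Where a parameter is log-transformed under SAP 3.2.2.4, the paired difference is a log ratio. Report the back-transformed ratio for that parameter and label it as such.
4. If a relative figure is wanted for plugs score, give the ratio of group means (Week 13 mean over Week 0 mean) as a labelled supplement. It keeps the participants whose baseline is zero.

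The cost is a few lines in the SAP or a further addendum entry. No new data are needed, and a lobe model already programmed from Equation 1 needs no change.
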